7.2.4.2. Doxorubicin Dose Adjustments

The dose adjustments and delays for doxorubicin apply to patients treated with olaratumab plus doxorubicin.

7.2.4.2.1. Hematologic Toxicity

Doxorubicin will not be administered if the patient's ANC is $<750/\text{mm}^3$ or if the platelet count is $<75,000/\text{mm}^3$. When necessary, the next treatment cycle should be delayed until the ANC is $\geq750/\text{mm}^3$ and the platelet count is $\geq75,000/\text{mm}^3$ and nonhematologic toxicities have resolved. For patients who experience Grade ≥3 neutropenic fever or infection, doxorubicin should be held until resolved and doxorubicin should be administered at the full dose at investigator's discretion with recommended use of prophylactic G-CSFs. If a patient experiences a second incidence of neutropenic fever/infection, then doxorubicin should be reduced to 28 mg/m^2 on Day 1 and Day 2 will be necessary (75% of the starting dose). If used, dexamethasone should be adjusted to maintain a 10:1 ratio with doxorubicin. Therapeutic and prophylactic use of Neulasta[®] (pegfilgrastim) or other G-CSFs will be allowed per current American Society of Clinical Oncology (ASCO; Smith et al. 2006) and National Comprehensive Cancer Network (NCCN 2015) guidelines or at the investigator's discretion. For patients with Grade 4 ANC without fever/infection, retreatment will be allowed at the investigator's discretion with the full dose of doxorubicin (37.5 mg/m^2 on Day 1 and Day 2) with recommended use of G-CSFs per current ASCO guidelines (Smith et al. 2006). See [Table JGDN.7.6](#) for doxorubicin dose modification for neutropenia.

Table JGDN.7.6. General Guidelines for Doxorubicin Dose Modification Due to Neutropenia

Toxicity	Required Dose Modification ^a
ANC <750/mm ³	No doxorubicin administered; treatment cycle delayed
At retreatment:	
If Grade ≥ 3 neutropenic fever/infection has occurred	Retreatment with doxorubicin at full dose at investigator's discretion with recommended use of prophylactic G-CSFs
Grade 4 ANC without fever/infection	
Second incidence of either:	
1) Grade ≥ 3 neutropenic fever/infection	Reduce to approximately 28 mg/m ² doxorubicin on Day 1 and Day 2
2) Grade 4 neutropenia lasting longer than 1 week	

Abbreviations: ANC = absolute neutrophil count; G-CSFs = granulocyte colony-stimulating factors.

a Dexrazoxane should be adjusted to maintain a 10:1 ratio with doxorubicin.

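### For a second afebrile Grade 4 neutropenia lasting over a week, the Protocol 7.2.4.2.1 text can be read as permitting full-dose doxorubicin while Table JGDN.7.6 calls for a reduction, and neither says which governs

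*Protocol*

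**What the plan says.** Both rules are in Protocol Section 7.2.4.2.1 (doxorubicin, hematologic toxicity).

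- **Text, afebrile Grade 4:** "For patients with Grade 4 ANC without fever/infection, retreatment will be allowed at the investigator's discretion with the full dose of doxorubicin". The sentence recommends growth-factor support. It does not say whether it covers a first episode only, or how long the episode may last.
- **Text, second incidence:** "If a patient experiences a second incidence of neutropenic fever/infection, then doxorubicin should be reduced", to 28 mg/m² on each of Days 1 and 2, described as 75% of the starting dose. No other second-incidence trigger appears in the text.
- **Table JGDN.7.6, full-dose row:** covers afebrile Grade 4 ANC, again with no limit on number or duration.
- **Table JGDN.7.6, next row:** "Second incidence of either" of two events: Grade ≥3 neutropenic fever or infection, and "2) Grade 4 neutropenia lasting longer than 1 week". The action is "Reduce to approximately 28" mg/m² on Days 1 and 2.

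The action column is headed "Required Dose Modification", but the table's title calls its contents general guidelines. The text ends by referring the reader to the table and does not rank the two.

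**The concern.** The case in question is a child on the doxorubicin arm with a second Grade 4 neutropenia, lasting more than a week, without fever or infection. A site relying on the text could retreat at full dose and consider itself compliant. A site relying on the table would reduce and regard the first site's choice as a departure from a required modification.

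The first consequence is for the patient, because the doxorubicin dose in later cycles would depend on how the section is read. Protocol Section 7.2.4.2.2 itself notes that cardiotoxicity risk rises with cumulative exposure.

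The second consequence is for reporting. Four SAP outputs depend on the rule:

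- counts of dose reductions (Section 5.7);
- doxorubicin dose intensity (Section 5.9.1);
- the listing of adverse events that led to dose modification (Section 5.9.2);
- dosing errors counted as important deviations (Section 5.5).

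If sites use different readings, these outputs mix two rules, and the same conduct may or may not be recorded as a deviation.

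**Working it through.** **Inputs.** Starting dose 37.5 mg/m² on Days 1 and 2; at most 6 doxorubicin cycles or 450 mg/m² (Protocol 7.2.2 and Table JGDN.7.1). Reduced dose 28 mg/m² on Days 1 and 2 (7.2.4.2.1 and Table JGDN.7.6). Planned doxorubicin intensity 25 mg/m²/week (SAP 5.9.1).

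**The plan's own figures reproduce.** 0.75 × 37.5 = 28.125, rounded to 28 (28 / 37.5 = 74.7%). 6 × 2 × 37.5 = 450 mg/m². 2 × 37.5 / 3 = 25 mg/m²/week.

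**The readings side by side**

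| Event | Text | Table JGDN.7.6 |
|---|---|---|
| First afebrile Grade 4 episode | full dose at discretion | full dose at discretion |
| Second neutropenic fever/infection | reduce | reduce |
| Second Grade 4 episode over 1 week, no fever/infection | not addressed separately; the general sentence permits full dose | reduce |

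Only the last row differs.

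**Per cycle.** Full: 2 × 37.5 = 75 mg/m². Reduced: 2 × 28 = 56 mg/m². Difference: 19 mg/m², and 19 / 75 = 25.3%. Weekly intensity at the reduced dose is 56 / 3 = 18.67 mg/m²/week, so relative dose intensity for that cycle is 18.67 / 25 = 74.7% rather than 100%.

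**Over six cycles.** Assume all six cycles are given, the second episode occurs in doxorubicin cycle k, and the reduction applies from cycle k + 1. The total is 75k + 56(6 − k).

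| k | Reduced-reading total (mg/m²) | Below 450 by |
|---|---|---|
| 2 | 150 + 224 = 374 | 76 (16.9%) |
| 3 | 225 + 168 = 393 | 57 (12.7%) |
| 4 | 300 + 112 = 412 | 38 (8.4%) |
| 5 | 375 + 56 = 431 | 19 (4.2%) |

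Cycle 2 is the earliest cycle considered for a second episode. An episode in cycle 6 leaves no later doxorubicin cycle to change.

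**The case against.** The strongest reply is that the text omits a trigger and does not state an opposing rule. It never mentions a second prolonged episode, it permits full dose without requiring it, and it sends the reader to the table. The table's own full-dose row is equally unlimited and is followed by the second-incidence row, so both can be read as a general rule with an exception after it. An investigator who reduces under the table does not breach the text. All of this stands, and it is why the discrepancy is a possible reading and not a flat contradiction.

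It does not close the gap. The cross-reference sets no precedence, and the table is a set of guidelines by title but required by column heading. The protocol does limit duration where it intends to: the matching full-dose row for olaratumab (Table JGDN.7.4) is confined to episodes of a week or less.

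Three stronger inferences are tempting, and the documents do not support them.

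- **That the discrepancy shifts when the 450 mg/m² limit is reached, and so when participation ends.** Six full-dose cycles total exactly 450, and the six-cycle limit also applies at the reduced dose, so both readings stop doxorubicin at cycle six. Whether participation then ends is itself unsettled: Protocol 6.2 allows olaratumab to continue alone after chemotherapy, while the Parts A and B doxorubicin schedule in Attachment 1 does not.
- **That the event is not rare, because 35.9% of the adult combination arm had Grade ≥4 neutropenia (Table JGDN.5.2).** That figure is a consolidated term that includes leukopenia. It counts any episode of any duration, in adults given doxorubicin 75 mg/m² on Day 1 only. It says nothing about second, prolonged, afebrile episodes in children.
- **That the DLT endpoint is compromised.** Combination DLTs are judged in the first combination cycle (Protocol 7.2.3.2), and this rule generally alters doses after it.

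**Conclusion.** The inconsistency is real and narrow. For one defined event, the text can be read as leaving full dose to discretion while the table calls for a reduction, and nothing says which prevails. It could mean 75 or about 56 mg/m² per cycle for the same child, 25% apart. The cumulative gap is 19 to 76 mg/m² (4% to 17%) on the stated assumptions: six cycles given, and a second episode between doxorubicin cycles 2 and 5. The 17% is the largest value in that range, not a typical one.

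How often the event will occur cannot be determined from the documents. The analyses are descriptive (SAP 5.2), so no test or sample size is affected. The correction is still worth making, because the rule governs dosing of children and determines what is counted as a reduction or a deviation.

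**What to change.** Reconcile the Section 7.2.4.2.1 text with Table JGDN.7.6 for a second Grade 4 neutropenia lasting over a week without fever or infection. State whether the text's full-dose sentence is limited by episode number or duration, and whether text or table governs. Which rule applies is for the sponsor's clinical team; this review takes no position.

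In the clinical study report, list any doxorubicin-arm patient who met this situation and was treated under the other reading, so that dose reductions, relative dose intensity and deviations can be interpreted.

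The cost is about one sentence of protocol wording and a short listing from dosing and laboratory data already collected. Sample size and planned analyses do not change.

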7.2.4.2.2. Cardiac Monitoring for Doxorubicin-Associated Cardiotoxicity

Cardiotoxicity is a recognized risk of doxorubicin that increases with higher cumulative drug exposure. Cardiac monitoring is conducted by a combination of monitoring of clinical parameters, ECG, and ECHO / MUGA scan.

ECG changes, arrhythmias, tachycardia, and/or chest pain should be managed based on the specific findings.

An ECHO/MUGA scan is required within 28 days prior to first dose of study drug for all patients receiving doxorubicin. Thereafter, ECHO or MUGA scans must be performed at the end of Cycles 2, 4, and 6 and when clinically indicated. If doxorubicin cardiotoxicity has been observed, an ECHO or MUGA should be performed at the 30-day follow-up visit. Additional ECHO/MUGA may be performed if clinically indicated or at the investigator's discretion.

If there is a decrease in LVEF to or below 40% or an absolute decrease of 20%, then doxorubicin will be discontinued. If there is an absolute decrease in the shortening fraction of $>10\%$ or the shortening fraction is below 29%, then doxorubicin will be discontinued. Doxorubicin should also be discontinued if the patient develops Grade 3 or 4 left ventricular systolic dysfunction (symptomatic CHF). If doxorubicin is discontinued for the above changes in LVEF, olaratumab should also be discontinued.

The diagnostic method used at baseline for cardiovascular assessments (for example, ECHO or MUGA scans) should be the same method used throughout the study, unless there is clinical or instrumental evidence that further investigations are needed.

7.2.4.2.3. Hepatic Impairment

Doxorubicin is contraindicated in patients with severe hepatic impairment (Child-Pugh Class C or serum bilirubin >5.0 mg/dL).

Decrease the dose of doxorubicin in patients with elevated serum total bilirubin concentrations as noted in [Table JGDN.7.7](#).

Table JGDN.7.7. General Guidelines for Doxorubicin Dose Modification Due to Elevated Serum Total Bilirubin Concentrations

Serum Bilirubin Concentration	Doxorubicin Dose Reduction
>1.5 to 3 mg/dL	50% of initial dose
3.1 to 5 mg/dL	25% of initial dose
Greater than 5 mg/dL	Do not initiate doxorubicin Discontinue doxorubicin

7.2.4.3. Vincristine Dose Adjustments

The dose adjustments and delays for vincristine apply to patients treated with olaratumab plus vincristine and irinotecan.

7.2.4.3.1. Hematologic Toxicity

Vincristine does not appear to have any constant or significant effect upon the platelets or the red blood cells; however, anemia and thrombocytopenia have been reported. Due to concerns of neurotoxicity, the ASCO guideline recommends that vincristine be capped at a maximum dose of 2 mg. No dose adjustment is required. Therapeutic and prophylactic use of Neulasta (pegfilgrastim) or other G-CSFs will be allowed according to the current ASCO (Smith et al. 2006) and NCCN guidelines (NCCN 2015) or at the investigator's discretion.

7.2.4.3.2. Nonhematologic Toxicity

Table JGDN.7.8 provides the general guidelines for dose modifications of vincristine due to toxicity.

7.2.4.3.2.1. Neurologic Toxicity

Vincristine-related sensory and motor neuropathies are common and are cumulative. Monitor patients for symptoms of neuropathy, such as hypoesthesia, hyperesthesia, paresthesia, hyporeflexia, areflexia, neuralgia, jaw pain, decreased vibratory sense, cranial neuropathy, ileus, burning sensation, arthralgia, myalgia, muscle spasm, or weakness, both before and during treatment. Orthostatic hypotension may occur. The risk of neurologic toxicity is greater if vincristine is administered to patients with preexisting neuromuscular disorders or when other drugs with risk of neurologic toxicity are being given. The most frequent manifestations of nervous system toxicity are as follows:

Peripheral neuropathy, the earliest indication of which is the depression of the Achilles reflex. Later loss of other deep tendon reflexes occurs and is accompanied by peripheral paresthesias, pain, and tingling. If therapy is prolonged or high doses are administered, wrist and foot drop, ataxia, a slapping gait, and difficulty in walking may occur. Young children may refuse to walk due to extremity pain.

Cranial nerve neuropathy may lead to vocal cord paresis or paralysis (hoarseness, weak voice), ocular motor nerve dysfunction (ptosis, strabismus), bilateral facial nerve palsies, or jaw pain. Severe jaw pain can occur within a few hours of the first dose of vincristine. Cranial nerve toxicities tend to be bilateral and reversible when treatment with vincristine is discontinued.

Autonomic neuropathy is manifested as constipation (which can be severe), abdominal pain, urinary retention, and paralytic ileus. Laxatives or stool softeners should be considered routinely to prevent constipation. These symptoms resolve with time and may not occur with subsequent treatment. If bladder atony occurs, vincristine should be held until symptoms resolve. Worsening neuropathy requires dose delay, reduction, or discontinuation.

Table JGDN.7.8. General Guidelines for Dose Modification of Vincristine due to Toxicity

Toxicity/Worst Counts in Cycle	Vincristine Dose Reduction
Neurotoxicity	
Grade 1 or 2	Full dose
Grade 3 or 4	Hold until Grade ≤ 1 then 50% of initial dose ^a
Severe paralytic ileus	Hold until normal bowel movement then 50% of initial dose
Grade 3 other related nonhematologic/organ toxicity	Hold
Grade 4 other related nonhematologic/organ toxicity	Discontinue

^a Reescalation to 75% or full dose should be considered at the start of each vincristine containing cycle based on patient's symptoms.

7.2.4.3.2.2. Hepatic Toxicity

Fatal liver toxicity and elevated levels of aspartate aminotransferase have occurred with vincristine use. Monitor hepatic function tests. Reduce or interrupt vincristine for hepatic toxicity (Table JGDN.7.9).

Table JGDN.7.9. General Guidelines for Vincristine Dose Modification Due to Elevated Serum Total Bilirubin Concentrations

Serum Bilirubin Concentration	Vincristine Dose Reduction
<2.1 mg/dL	Full dose
2.1 to 4 mg/dL	50% of initial dose
4.1 to 6 mg/dL	25% of initial dose
Greater than 6 mg/dL	Do not initiate vincristine Discontinue vincristine

7.2.4.4. Irinotecan Dose Adjustments

Dose levels and adjustments for irinotecan are shown in Table JGDN.7.10. General guidelines for irinotecan dose modifications are shown in Table JGDN.7.11.

7.2.4.4.1. Hematologic Toxicities

Irinotecan may cause severe myelosuppression and deaths due to sepsis following severe myelosuppression. Therapy should be temporarily discontinued if neutropenic fever occurs or if the ANC is $<750/\text{mm}^3$. The dose of irinotecan should be reduced according to

Table JGDN.7.11. Patients with abnormal glucuronidation of bilirubin, such as Gilbert's syndrome, may also be at greater risk of myelosuppression when receiving irinotecan. A new cycle of therapy should not begin until the granulocyte count has recovered to $\geq 750/\text{mm}^3$ and the platelet count has recovered to $\geq 75,000/\text{mm}^3$. Treatment should be delayed 1 to 2 weeks to

allow for recovery from treatment-related toxicities. If the patient has not recovered after a 2-week delay, consideration should be given to discontinuing irinotecan.

7.2.4.4.2. Diarrhea and Cholinergic Reactions

Irinotecan may cause severe, dose-limiting, and potentially fatal diarrhea. Early diarrhea has occurred during or shortly after infusion and may be accompanied by symptoms of rhinitis, increased salivation, miosis, lacrimation, diaphoresis, flushing, and abdominal cramping.

Atropine 0.01 mg/kg IV (maximum dose: 0.4 mg) may be used to prevent or treat symptoms of early diarrhea. Late diarrhea has occurred >24 hours after irinotecan administration and can be prolonged, leading to life-threatening dehydration and electrolyte imbalance. Treat late diarrhea promptly with loperamide until a normal pattern of bowel movements returns; fluid and electrolyte replacement may be needed for dehydration. Provide antibiotic support (cefixime has been used in children whose diarrhea persisted >24 hours despite loperamide) if patient develops persistent diarrhea, ileus, fever, or severe neutropenia. Interrupt or reduce subsequent irinotecan doses if NCI CTCAE Grade 3 (increase of 7-9 stools daily, or incontinence, or severe cramping) or Grade 4 (increase ≥ 10 stools daily, grossly bloody stool, or need for parenteral support) late diarrhea occurs. Cases of colitis complicated by ulceration, bleeding, ileus, and infection have been reported. Renal impairment and acute renal failure have been reported, possibly due to dehydration secondary to diarrhea. A new cycle of therapy should not begin until treatment-related diarrhea is fully resolved. If the patient has not recovered after a 2-week delay, consideration should be given to discontinuing irinotecan.

Table JGDN.7.10. Dose Levels and Adjustments for Irinotecan

Dose at Enrollment	Dose Reduction		
	-1 dose level	-2 dose levels	3 dose levels
50 mg/m ² /d	25% reduction	50% reduction	discontinue irinotecan

Table JGDN.7.11. General Guidelines for Dose Modification of Irinotecan due to Toxicity

Toxicity	During a Cycle of Therapy
Neutropenia	
Grade 3 (500 to 749/mm ³)	Hold dose until resolved to $\geq 750/\text{mm}^3$; no dose reduction
Grade 4 (<500/mm ³)	Hold dose until resolved to $\geq 750/\text{mm}^3$ and then decrease by 1 dose level
Neutropenic fever	
Diarrhea	
Grade 2 (4–6 stools/day $>$ pretreatment)	Hold dose; no dose reduction
Grade 3 (7–9 stools/day $>$ pretreatment)	Hold dose until resolved to ≤ 2 and then decrease by 1 dose level
Grade 4 (≥ 10 stools/day $>$ pretreatment)	Hold dose until resolved to ≤ 2 and then decrease by 2 dose levels
Other nonhematologic toxicities	
Grade 2	Hold dose; no dose reduction
Grade 3	Hold dose until resolved to ≤ 2 and then decrease by 1 dose level
Grade 4	Hold dose until resolved to ≤ 2 and then decrease by 2 dose levels

7.2.4.5. Ifosfamide Dose Adjustments

7.2.4.5.1. Urotoxic Effects

The incidence of urotoxic effects without an uroprotector can be up to 40% and is dose dependent; coadministration with mesna and adequate hydration are mandatory. Patients may present with hematuria, symptomatic cystitis, or bladder fibrosis. Past or concomitant radiation of the bladder or busulfan treatment may increase the risk of hemorrhagic cystitis. Several methods of treatment for established hematuria have been described: bladder irrigation with water or normal saline, intravesical instillation of astringents (alum, silver nitrate), systemic administration of antifibrinolytics (aminocaproic acid, tranexamic acid), cystoscopy to evacuate the bladder of clots, continuous bladder irrigation, and intravesical prostaglandins. For severe or refractory hematuria, intravesical formalin, phenol, or prostaglandin has been used \pm surgical intervention (electrocautery, cryosurgery, diversion of urine flow, hypogastric artery ligation, or cystectomy). Ifosfamide should be discontinued or dose reduced for macroscopic hematuria.

7.2.4.5.2. Proximal Tubular Damage

Glomerular, proximal, or distal tubular impairment may all occur, often in combination and may progress even after ifosfamide has been discontinued. Proximal tubular damage often presents as Fanconi syndrome with low serum bicarbonate, proteinuria, glucosuria, aminoaciduria, and hypochloremic metabolic acidosis. Risk factors for the development of nephrotoxicity include age less than 5 years; preexisting renal impairment; prior treatment with cisplatin; concurrent use of nephrotoxic drugs, reduced renal reserve (unilateral nephrectomy, renal radiation); hydronephrosis; and total cumulative dose. Renal impairment may increase the risk of myelosuppression and possibly, cardiotoxicity. Mesna does not appear to be protective against

the proximal tubular abnormalities induced by ifosfamide. Dose modifications of ifosfamide due to renal impairment are shown in [Table JGDN.7.12](#).

Table JGDN.7.12. Dose Modification of Ifosfamide due to Renal Impairment

Creatinine Clearance (mL/Min)	Ifosfamide Dose Reduction
>60	Full dose
40-60	75% of initial dose
20-40	50% of initial dose
<20	Discontinue

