6.1.1. Inclusion Criteria

Patients may be included in the study if they meet all of the following criteria during screening prior to first dose of study drug.

- [1] The patient must have histological or cytological evidence of a diagnosis of solid tumor, excluding lymphomas and melanoma, but including central nervous system (CNS) tumors, that is relapsed or refractory, not be amenable to curative treatment, and for whom chemotherapy with doxorubicin, vincristine/irinotecan, or ifosfamide is deemed appropriate by the investigator. For patients with CNS tumors, neurologic deficits in patients with CNS tumors must have been stable for at least 7 days prior to study enrollment.
- [2] The patient has the presence of measurable and/or nonmeasurable but evaluable disease as defined by the Response Evaluation Criteria In Solid Tumors (RECIST Version 1.1) (Eisenhauer et al. 2009; refer to [Attachment 8](#)). Response Assessment in Neuro-Oncology (RANO) Criteria (Wen et al. 2010) or Macdonald Criteria (Macdonald et al. 1990) should be used for CNS tumors.
- [3] The patient is <18 years of age at the time of first dose of study drug.
- [4] The patient, or patient's parent/guardian, has given written informed consent and authorization for release of health information for research prior to any study-specific procedures being performed.
- [5] The patient has a Lansky (<16 years of age; Lansky et al. 1987) or Karnofsky (≥ 16 years of age; Karnofsky et al. 1948) performance score of at least 50.
- [6] The patient has adequate hematologic, organ, and coagulation function ≤ 2 weeks (14 days) prior to first dose of study drug:
 - Absolute neutrophil count (ANC) $\geq 750/\text{mm}^3$. Granulocyte colony-stimulating factor (G-CSF) cannot be administered ≤ 1 week (7 days) prior to first dose of study drug. Pegfilgrastim cannot be administered ≤ 2 weeks (14 days) prior to first dose of study drug.

- Platelets $\geq 75,000/\text{mm}^3$. Platelet transfusion to meet this enrollment criterion is not allowed within the preceding 5 days of first dose of study drug.
- Hemoglobin $\geq 8 \text{ g/dL}$. Transfusions with packed red blood cells is allowed.
- Total bilirubin (sum of conjugated + unconjugated) $\leq 1.5 \times$ upper limit of normal (ULN) for age.
- Alanine aminotransferase (ALT) and aspartate aminotransferase (AST) $\leq 3.0 \times$ ULN. If the liver has tumor involvement, AST and ALT equaling $\leq 5.0 \times$ ULN are acceptable.

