- Serum creatinine is based on age/gender as follows:

Age	Maximum Serum Creatinine (mg/dL)	
	Male	Female
1 month to < 6 months	0.4	0.4
6 months to < 1 year	0.5	0.5
1 to < 2 years	0.6	0.6
2 to < 6 years	0.8	0.8
6 to < 10 years	1.0	1.0
10 to < 13 years	1.2	1.2
13 to < 16 years	1.5	1.4
$\geq 16 \text{ years}$	1.7	1.4

The threshold creatinine values in this table were derived from the Schwartz formula for estimating glomerular filtration rate ([Attachment 6](#)).

- The patient has an adequate coagulation function as defined by International Normalized Ratio ≤ 1.5 or prothrombin time $\leq 1.5 \times$ ULN, and partial thromboplastin time $\leq 1.5 \times$ ULN if not receiving anticoagulation therapy. For patients receiving anticoagulants, exceptions to these coagulation parameters are allowed if they are within the intended or expected range for their therapeutic use. Patients must have no history of active bleeding (defined as within 14 days of first dose of study drug) or pathological condition that carries a high risk of bleeding (for example, tumor involving major vessels or known esophageal varices).

[7] Female patients of child-bearing potential must have a negative serum pregnancy test within 7 days prior to Cycle 1 Day 1.

- [8] Both female and male patients of child-bearing potential must agree to use highly effective contraceptive precautions during the trial and up to 3 months following the last dose of olaratumab, or longer if appropriate for other study drugs according to their label. A highly effective method of birth control is defined as one that results in a low failure rate (that is, <1% per year) when used consistently and correctly, such as implants, injectables, combined oral contraceptives, some intrauterine contraceptive devices, sexual abstinence, or a vasectomized partner.
- [9] Patients must have fully recovered from the acute toxic effects of all prior anticancer therapies or must adhere to post-treatment conditions as follows:
 - Myelosuppressive chemotherapy: at least 21 days after the last dose of myelosuppressive chemotherapy (or 42 days if prior nitrosourea)

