7.2.2. Dosing Schedule

If any study drug is discontinued (olaratumab or chemotherapy), the patient will be discontinued from the trial. A change of body weight $\geq 10\%$ (increase or decrease) from baseline will result in re-calculation of dose to be administered.

The following treatments will be administered in this study every 3-week (21-day) ± 3 day cycle ([Table JGDN.7.1](#) and [Table JGDN.7.2](#)).

Part A:

Cycle 1

Olaratumab as IV infusion on Day 1 and Day 8 (at 15 mg/kg)

Cycle 2 and beyond

Olaratumab as IV infusion on Day 1 and Day 8 (at 15mg/kg, or 10 mg/kg if de-escalated),

AND

Doxorubicin as IV infusion on Day 1 and Day 2 (at 37.5 mg/m²; up to 6 cycles or a cumulative dose of 450 mg/m²)

OR

Vincristine as IV on Day 1 and Day 8 (patients ≥ 10 kg: 1.5 mg/m², patients <10 kg: 0.05 mg/kg. Dose is capped at 2 mg) plus irinotecan as IV on Days 1, 2, 3, 4, 5 (at 50 mg/m²),

OR

Ifosfamide as IV on Days 1, 2, 3, 4, and 5 (at 2.8 g/m²; up to 6 cycles or a cumulative dose of 84 g/m²). Treatment beyond 84 g/m² requires consultation with the Lilly CRP/CRS.

Part B:

Cycle 1

Olaratumab as IV infusion on Day 1 and Day 8 (at 20 mg/kg)

Cycle 2 and beyond

Olaratumab as IV infusion on Day 1 and Day 8 (at 20 mg/kg),

AND

Doxorubicin as IV infusion on Day 1 and Day 2 (at 37.5 mg/m²; up to 6 cycles or a cumulative dose of 450 mg/m²)

OR

Vincristine as IV on Day 1 and Day 8 (patients ≥ 10 kg: 1.5 mg/m², patients <10 kg: 0.05 mg/kg. Dose is capped at 2 mg) plus irinotecan as IV on Days 1, 2, 3, 4, 5 (at 50 mg/m²),

OR

Ifosfamide as IV on Days 1, 2, 3, 4, and 5 (at 2.8 g/m²; up to 6 cycles or a cumulative dose of 84 g/m²). Treatment beyond 84 g/m² requires consultation with the Lilly CRP/CRS.

Part C:

All Cycles

Olaratumab as IV infusion on Day 1 and Day 8 (at 20 mg/kg),

AND

Doxorubicin as IV infusion on Day 1 and Day 2 (at 37.5 mg/m²; up to 6 cycles or a cumulative dose of 450 mg/m²)

OR

Vincristine as IV on Day 1 and Day 8 (patients \geq 10 kg: 1.5 mg/m², patients <10 kg: 0.05 mg/kg. Dose is capped at 2 mg) plus irinotecan as IV on Days 1, 2, 3, 4, and 5 (at 50 mg/m²),

OR

Ifosfamide as IV on Days 1, 2, 3, 4, and 5 (at 2.8 g/m²; up to 6 cycles or a cumulative dose of 84 g/m²). Treatment beyond 84 g/m² requires consultation with the Lilly CRP/CRS.

Table JGDN.7.1. Treatment Regimens/Dosing Schedule (Parts A and B)

Study Drug		Dose	Route	Timing

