Attachment 5. Protocol JGDN Recommendations for Reporting Serious Adverse Events

Recommendations for Reporting Serious Adverse Events

When contacting Lilly to report a SAE, please have the following information available:

Patient Demographics

- patient identification (number), sex, date of birth, origin, height, and weight

Study Identification

- full trial protocol number, investigator's name, investigator's number

Study Drug

- drug code or drug name, unit dose, total daily dose, frequency, route, start dose, cycle details, start date and last dose date (if applicable)

Adverse Event

- description, date of onset, severity, treatment (including hospitalization), action taken with respect to study drug, clinical significance, test and procedure results (if applicable)

Relationship to Study Drug & Protocol Procedures

Concomitant Drug Therapy

- indication, total daily dose, duration of treatment, start date, action taken

In Case of Death

- cause, autopsy finding (if available), date, relationship to study drug and protocol procedures.

**Attachment 6. Protocol JGDN Creatinine Clearance
Formula**

Protocol JGDN will use the Schwartz formula for the determination of creatinine clearance.

All Females and Pre-adolescent Males:

$$C_{cr} \text{ (mL/min/1.73 m}^2\text{)} = 0.55 \times \text{Height (cm)}/S_{cr} \text{ (mg/dL)}$$

Adolescent Males:

$$C_{cr} \text{ (mL/min/1.73 m}^2\text{)} = 0.70 \times \text{Height (cm)}/S_{cr} \text{ (mg/dL)}$$

Note: C_{cr} = creatinine clearance and S_{cr} = serum creatinine

Source: Schwartz et al. 1976; Schwartz and Gauthier 1985.

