#### Doxorubicin:

- Duration of treatment (weeks) = ([Date of last dose – date of first dose] + 21) ÷ 7
- Cumulative dose (mg) = Sum of all doses
- Cumulative dose level (mg/m^2) = Sum of (dose administered at each infusion [mg] ÷ Last available body surface area [BSA] [m^2] prior to that infusion)
- BSA (m^2) = 0.007184 \* weight (kg) ^0.425 \* height (cm) ^0.725

- Weekly dose intensity (mg/m^2/week) = (Cumulative dose level) ÷ (Duration of treatment)
- Planned weekly dose intensity (mg/m^2/week) = 2 x 37.5 mg/m^2/ 3 weeks=25
- Relative dose intensity (%)=(Weekly dose intensity) ÷ (Planned weekly dose intensity) x 100

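### The ifosfamide renal dosing table is in mL/min, but the protocol's only clearance formula gives mL/min/1.73 m²; a clearance of 40 also falls in two dose rows

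*Protocol*

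**What the plan says.** Protocol section 7.2.4.5.2 introduces Table JGDN.7.12 with "Dose modifications of ifosfamide due to renal impairment are shown in". The table's first column is headed "Creatinine Clearance (mL/Min"). Its four rows are: above 60, full dose; 40-60, 75% of the initial dose; 20-40, 50%; below 20, discontinue.

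Attachment 6 states: "Protocol JGDN will use the Schwartz formula for the determination of creatinine clearance". Both of its equations (constant 0.55 for all females and pre-adolescent males, 0.70 for adolescent males) give a result in mL/min/1.73 m².

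The same formula underlies the entry creatinine limits in section 6.1.1: "The threshold creatinine values in this table were derived from the Schwartz formula for estimating glomerular filtration rate".

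Section 7.2.2 adds: "If any study drug is discontinued (olaratumab or chemotherapy), the patient will be discontinued from the trial".

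Section 7.2.4.5.2 does not cite Attachment 6. Neither the protocol nor the SAP gives another clearance method or a conversion to absolute mL/min.

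**The concern.** The dosing table and the only formula that can feed it are in different units. A site can enter the Schwartz result directly and disregard the printed unit, or it can multiply by BSA/1.73 to obtain the unit in the header. The text supports either course.

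At adult body size the choice hardly matters. This trial, however, has no lower age bound beyond "The patient is <18 years of age at the time of first dose of study drug", and its creatinine limits start at 1 month. In a small child, conversion can move normal normalised clearance into a reduced-dose row. At the highest creatinine allowed at entry it can reach the discontinue row, and section 7.2.2 then removes the child from the trial. Under section 7.6.1, a child removed before completing the combination cycle without a DLT is also non-evaluable for that combination.

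The readings diverge most in the age group that the protocol itself flags: "Risk factors for the development of nephrotoxicity include age less than 5 years". Separately, 40 is printed as an endpoint of two adjacent rows.

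**Working it through.** **Inputs.** The Schwartz formula is from Attachment 6, the dose rows from Table JGDN.7.12, and the creatinine maxima from section 6.1.1, criterion 6. The ifosfamide dose is from section 7.2.2 (2.8 g/m² on Days 1 to 5). The BSA formula is from SAP section 5.9.1, because the protocol gives none. Heights and weights are assumptions, chosen to span the age range.

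**Formulas.**
- Normalised clearance = 0.55 × height (cm) / creatinine (mg/dL), in mL/min/1.73 m²
- BSA = 0.007184 × weight^0.425 × height^0.725
- Absolute clearance (mL/min) = normalised clearance × BSA/1.73

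**Worked case: 87 cm, 12 kg, creatinine 0.5.** Normalised: 0.55 × 87 / 0.5 = 95.7. BSA = 0.526 m², so the ratio is 0.526/1.73 = 0.304. Absolute: 95.7 × 0.304 = 29.1. Direct entry gives full dose; the printed unit gives 50%.

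| Assumed child | Creatinine | Normalised → row | Absolute → row |
|---|---|---|---|
| 70 cm, 8.5 kg | 0.5 (entry maximum, 6 months to <1 year) | 77.0 → full | 17.3 → discontinue |
| 87 cm, 12 kg | 0.3 | 159.5 → full | 48.5 → 75% |
| 87 cm, 12 kg | 0.5 | 95.7 → full | 29.1 → 50% |
| 87 cm, 12 kg | 0.8 (entry maximum, 2 to <6 years) | 59.8 → 75% | 18.2 → discontinue |
| 100 cm, 16 kg | 0.8 (same entry maximum) | 68.8 → full | 26.1 → 50% |
| 102 cm, 16 kg | 0.6 | 93.5 → full | 36.1 → 50% |
| 125 cm, 25 kg | 1.0 (entry maximum, 6 to <10 years) | 68.8 → full | 37.2 → 50% |
| 163 cm, 55 kg, girl | 0.7 | 128.1 → full | 117.3 → full |

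**Full dose under the printed unit.** For the 87 cm child, an absolute clearance of 60 needs a normalised value of 60/0.304 = 197, that is, creatinine of 0.55 × 87 / 197 = 0.24. At an assumed normalised clearance of 120, absolute clearance is 60 or less whenever BSA is at most 60 × 1.73 / 120 = 0.865 m², so no such child gets full dose.

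**Discontinue under direct entry.** A normalised value of 20 at the entry creatinine limit requires a height of 20 × limit / 0.55: 29.1 cm at a limit of 0.8, and 50.9 cm at 1.4. No child in those age bands is that short, so direct entry does not reach this row at the entry limits.

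**Dose at stake per cycle.** Full dose is 5 × 2.8 = 14.0 g/m². The 75% row gives 10.5 g/m² and the 50% row 7.0 g/m².

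**Boundaries.** As printed, 60 falls only in the 75% row and 20 only in the 50% row. The value 40 falls in both, so either 10.5 or 7.0 g/m² complies.

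**The case against.** The strongest reply is that the protocol names one method and no conversion. The natural course is to compute the Schwartz value and read off the row. A site that converts adds a step nobody asked for, with a BSA formula the protocol does not supply. The entry limits point the same way: in the examples above, a child at the limit has a normalised value of about 60 to 77, close to the table's cut at 60. The converted reading also gives odd results, such as cutting a child with a Schwartz value of 160 to 75% for renal impairment, and a paediatric site would probably query that.

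This is persuasive about what the sponsor meant, and many sites probably do enter the Schwartz value. But the intention is inferred; the text does not state it, and a site that converts is following the unit printed in the header.

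Three narrower points have some force:
- The discontinue examples need a small child carrying the maximum creatinine of the age band. The 100 cm child at the same 0.8 mg/dL lands in the 50% row instead.
- The table is worded for patients already on ifosfamide. Applying it at the first ifosfamide cycle (Cycle 2 in Parts A and B, Cycle 1 in Part C) is a reading, and an investigator who believed clearance was 18 mL/min could choose another regimen.
- The overlap at 40 matters only for a value of exactly 40, and Table JGDN.7.14 shares boundaries in the same way.

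These points limit how often harm would follow. They do not remove the conflict.

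**Conclusion.** The concern holds and should be fixed. The unit in Table JGDN.7.12 does not match the only clearance formula in the protocol, and nothing reconciles them. Across the small body sizes tried, the two readings differ by one to three dose rows, and at adult size they agree. The largest consequence is discontinuation, and with it removal from the trial, of a child who met the entry creatinine limit.

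The conflict and the overlap at 40 are plain from the text. The size of the effect rests on assumed heights and weights and the SAP's BSA formula. How many sites would convert cannot be known from the documents. This is a fault in a dosing instruction; no effect on the DLT rules, the exposure-matching endpoint or any analysis has been shown. The overlap at 40 is a minor part of the point.

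**What to change.** Change the header of Table JGDN.7.12 to creatinine clearance in mL/min/1.73 m², Schwartz formula, Attachment 6. Make the bands exclusive: above 60, full dose; 40 to 60, 75%; 20 to <40, 50%; below 20, discontinue.

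The normalised unit is the right choice because ifosfamide is already dosed per m², so an unscaled clearance would count body size twice. It also matches the scale from which the entry limits were derived. If absolute mL/min was intended, the protocol should say so and give the conversion and cut-offs suited to children.

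The cost is one header and one band edit at the next amendment, with a note to sites meanwhile. For a site that already enters the Schwartz value directly, nothing changes except at exactly 40.
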